#### ***10.4.4 Safety Analyses***

The frequency of AEs, SAEs, adverse drug reactions (ADR), and suspected unexpected serious AE will be recorded. Additionally, counts of the number of laboratory values that fall outside of the normal range will be used to assess safety.

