#### 4.2.2 *Secondary Endpoints*

Safety endpoints will be captured through 6 months and will include the incidence of AEs including:

- deaths
- SAEs
- AEs leading to discontinuation
- common AEs
- AEs of special interest (injection site reactions and hepatic effects)
- laboratory abnormalities (absolute values and changes over time in laboratory parameters)
- the proportion of participants who discontinue treatment due to AEs

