#### ***7.2.3 Total amount of Blood to be collected***

The amount of blood drawn for the study is:

- Total LFT, EUC and FBC = 180.5 mL (18 x 9.5 mL)

- Pregnancy testing (Female participants only) = 4 mL (during the trial, a blood test will be used to confirm a positive urine result)
- Total blood samples for NTX / 6 $\beta$ N
  - 387 mL (43 x 9 mL)
- There is also the potential for further bloods to be taken on any un-scheduled visit for PK bloods (9 mL) and follow-up visit for outstanding AEs (LFT, EUC and FBC 9.5 mL) post end of trial.

The total scheduled blood collection is approximately 581.5 mL over the period of 196 days.

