### **7.3 STUDY SCHEDULE**

#### ***7.3.1 Screening Visit***

Participant shall be screened for inclusion and exclusion criteria and overall suitability for the study.

- Obtain informed consent for screening.
- Review medical history to determine eligibility based on inclusion/exclusion criteria.
- Review medications history to determine eligibility based on inclusion/exclusion criteria.
- Perform medical examinations, including Patient Health Questionnaire (PHQ-9), Beck Depression Inventory (BDI)-II, and C-SSRS to determine eligibility based on inclusion/exclusion criteria.
- Concomitant medication review
- Collect blood for LFT, FBE and EUC.
- Collect blood for NTX and 6 $\beta$ N measurement.
- Collect blood/urine for pregnancy test in female participants.

- Self-reported substance use and UDS

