#### **7.3.3.5 Vivitrol re-administration Day 28, 56, 84 & 112 ( $\pm 1$ day)**

There will be no intensive blood monitoring scheduled after administration of the 2nd, 3rd, 4th and 5th dose of Vivitrol as outlined in Table 7-1. In this instance, participants will be seen on an out-patient basis at Clinilabs for their re-administration of Vivitrol. Just prior to re-administration of Vivitrol, blood samples will be taken for: LFT, EUC & FBE; and NTX PK analysis to capture the Vivitrol trough level. The actual time of each PK sample collection shall be recorded relative to the re-administration of Vivitrol.

Participants will also be monitored for the following: AEs, PHQ-9, BDI-II, CSSRS, concomitant medication review, Vital signs, substance Use (Self report) and UDS. Where applicable a pregnancy test will also be conducted.

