## 8 ASSESSMENT OF SAFETY

### 8.1 SPECIFICATION OF SAFETY PARAMETERS

Safety will be assessed on the basis of:

- the incidence of death
- the incidence of SAEs
- the incidence AEs leading to discontinuation
- the incidence common AEs
- the incidence injection site reactions
- laboratory abnormalities indicating hepatic problems (absolute values and changes over time)

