#### ***10.4.7 Baseline Descriptive Statistics***

Baseline characteristics will be calculated using mean, standard deviation, median, interquartile range, percentages and 95% confidence intervals (where appropriate).

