#### ***10.4.11 Tabulation of Individual Response Data***

Individual PK and safety data will be tabulated for each time point and included in the appendices of the final study report.

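### The laboratory endpoint includes change over time, but the plan offers only a count of out-of-range values and appendix listings, so change has no planned analysis

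*Combined protocol and SAP*

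**What the plan says.** The secondary safety endpoints in 4.2.2 include "laboratory abnormalities (absolute values and changes over time in laboratory parameters". The synopsis and 3.2 carry the same item. Section 8.1 has a narrower one, restricted to the liver: "laboratory abnormalities indicating hepatic problems (absolute values and changes over time".

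For the analysis, 10.4.4 records the frequency of adverse events and then states that "counts of the number of laboratory values that fall outside of the normal range will be used to assess safety". Two other sections touch on these data:

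- 10.4.11: "Individual PK and safety data will be tabulated for each time point and included in the appendices of the final study report".
- 10.4.7: "Baseline characteristics will be calculated using mean, standard deviation, median, interquartile range, percentages and 95% confidence intervals (where appropriate". This covers baseline only.

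On collection, 7.3.1 lists for screening "Collect blood for LFT, FBE and EUC", and 7.3.3.5 says of the visits for doses 2 to 5: "Just prior to re-administration of Vivitrol, blood samples will be taken for: LFT, EUC & FBE; and NTX PK analysis to capture the Vivitrol trough level". Table 7-1 also marks safety bloods at the Day 140 to 142 admission and at Day 196, and none at Day 0.

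**The concern.** The endpoint sections ask for levels and trends. The analysis section answers with a tally of results outside the normal range. A tally has no time dimension and no reference to where a participant started, so it cannot describe change. It also treats a result just above the upper limit like one several times higher, although the protocol itself attaches importance to 3 times the limit (exclusion in 5.2, removal in 5.4.2.1) and names hepatic effects as an event of special interest.

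At stake is how the study describes the liver and general laboratory profile over six injections. If the count is the only summary, one person's repeated mild result can dominate it, and a modest shift across the whole group can leave little trace.

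**Working it through.** **Step 1. Set the endpoint beside the planned output.**

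| Part of the endpoint | Planned output |
|---|---|
| Occurrence of abnormalities | Count of values (10.4.4); adverse event tables when a finding is recorded as an event (10.4.5) |
| Values themselves | Individual listings in appendices (10.4.11); no summary by visit |
| Change over time | None |

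Sections 10.4.3 (accumulation, curves, substance use), 10.4.5 (adverse events), 10.4.7 (baseline) and 10.4.8 (safety review) were checked. None plans a by-visit laboratory summary, a change from baseline or a participant-level laboratory table, and none defines a laboratory baseline.

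**Step 2. Check that the data would support an analysis of change.** Table 7-1 marks scheduled safety bloods at screening, Days 28, 56, 84 and 112, the Day 140 to 142 admission and Day 196: 1 + 4 + 1 + 1 = 7 time points. That is 1 pre-dose and 6 post-dose. If blood is drawn on each of the three admission days, the total is 9, with 8 post-dose. Change from baseline can be calculated either way.

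Section 7.2.3 gives a different number: "Total LFT, EUC and FBC = 180.5 mL (18 x 9.5 mL". That line does not agree with itself (18 × 9.5 = 171; 19 × 9.5 = 180.5), and neither 18 nor 19 matches the 7 to 9 draws in Table 7-1. The passages need to be reconciled. The working below uses Table 7-1.

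**Step 3. See how the count behaves.** No denominator is stated. For 12 completers (10.5) the number of panels is 12 × 7 = 84, 12 × 9 = 108, or 12 × 18 = 216, depending on which passage is followed.

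The numerical liver exclusion in 5.2 is ALT or AST above 3 times the upper limit. A participant with a milder elevation judged not clinically important could therefore enter. If it stays stable, it adds 6 post-dose counts (7 with screening). Two participants with one value each above 3 times add 2. In values this is 6 against 2; in participants it is 1/12 against 2/12.

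Sampling is also unequal. Table 7-1 marks safety bloods at the adverse event follow-up visit, which 7.3.8 requires only for participants with ongoing events or laboratory abnormalities. Those already abnormal get extra chances to add counts.

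**Step 4. See what a shift within the range does.** A value that stays inside the range contributes zero however far it has moved. To show scale, assume (these figures are not in the documents) that ALT is normally distributed with SD 15% of the upper limit. The share above the limit is 1 − Φ((1 − mean)/0.15), and 12 participants × 6 post-dose points give 72 values.

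| Mean ALT, fraction of upper limit | z | Share above limit | Expected count of 72 |
|---|---|---|---|
| 0.50 | 3.33 | 0.04% | 0.03 |
| 0.75 | 1.67 | 4.8% | 3.4 |
| 0.90 | 0.67 | 25.2% | 18.2 |

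On these assumptions a 50% rise in the group mean (0.50 to 0.75) appears as about 3 values in 72, fewer than the 6 from the single stable participant in Step 3. A larger rise does show. The count is insensitive to moderate shifts, not blind to all of them.

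**The case against.** The strongest reply is that the count does not stand alone. Section 10.4.11 tabulates individual safety data at each time point. With at most 15 participants, a reader could follow each person's values in those tables. The endpoint item is also headed by abnormalities, and a count of out-of-range results addresses that part. It would be too strong to infer that the laboratory endpoint is not delivered at all.

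A reader might also infer that serious liver elevations would be hidden behind trivial ones. The documents do not support that:

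- Section 8.1.1.1 allows an abnormal laboratory finding to be an adverse event.
- Section 8.3 treats conditions present at screening as baseline and records deterioration as an event.
- Section 10.4.5 counts each participant once, at worst severity.
- Liver enzymes above 3 times normal are a removal criterion in 5.4.2.1, and events leading to discontinuation are listed by participant.

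Nor does 10.4.4 say that low and high results are pooled, or that the count ranks participants. It is silent on layout and presents the count as an addition to the adverse event frequencies.

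All of this stands, but it leaves the gap. The listings calculate and summarise nothing. The adverse event route covers only findings recorded as events, and 7.3.6 and 7.3.8 refer to laboratory abnormalities considered to be events, which implies that some are not. None of these routes describes change over time.

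**Conclusion.** The point holds in a limited form. Change over time is part of the stated endpoint and has no planned analysis. Values are listed but not summarised. The count that is planned is of values, without denominator, baseline or grading. One stable mild abnormality can add about 6 post-dose counts per parameter under Table 7-1 (8 if every Day 140 to 142 admission day is sampled), and a rise within the range is not counted.

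The 6 rests on Table 7-1 rather than on the conflicting draw total in 7.2.3. The in-range illustration rests on an assumed ALT distribution and shows direction and scale only. The textual gap depends on neither.

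This is a cheap improvement. The study is single-arm, states no hypotheses (10.2), and its primary PK result is unaffected. The documents do not support a conclusion that safety monitoring of participants is compromised.

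**What to change.** In 10.4.4:

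1. Define laboratory baseline as the last pre-dose value, which is screening under Table 7-1.
2. For each parameter, summarise observed value and change from baseline descriptively at each scheduled visit, with the number of participants contributing.
3. Report out-of-range results as n/N participants, separately for low and high.
4. For the liver tests to which it applies, give the number of participants by highest post-baseline multiple of the upper limit (≤1, >1–3, >3). This is a display only and changes no clinical rule. Name the tests: the 7.2.1 panel lists ALT but not AST, which the exclusion criterion in 5.2 uses.
5. State that early termination, unscheduled and follow-up values enter the worst-value display but not the by-visit summaries.
6. Keep the raw count of values as supplementary.

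The cost is two extra descriptive tables. No new sample, visit, hypothesis or change in sample size is needed. The draw count in 7.2.3 should be reconciled with Table 7-1 at the same time, so that the visits in the tables are unambiguous.

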#### ***10.4.5 Adverse Events***

After coding of AEs according to the Medical Dictionary for Regulatory Activity classification (MedDRA) and assignment to a system organ class and preferred term, all AEs recorded during the course of the trial will be listed by the participant number.

An AE will be considered as 'treatment emergent' if it occurred after the first drug administration of each period or if it was present prior to drug administration but exacerbated after the drug administration. All other adverse events will be considered "pre-treatment."

In the case where it is not possible to define an AE as being treatment emergent or not, the AE will be classified as treatment emergent as the most conservative approach.

A summary table describing all the TEAEs occurring during the trial will be produced overall and by treatment sequence using frequency of events and number and percentage of subjects experiencing these events. In addition, all TEAEs will be tabulated by intensity and relationship to drug in the same manner. Multiple occurrences of the same TEAE in one participant during the same treatment in the trial will be counted as multiple events in the frequency counts for adverse events. If a participant experiences more than one occurrence of the same TEAE during the same treatment in the trial, the participant will only be counted once using the worst severity and the strongest relationship.

All adverse events leading to trial or treatment discontinuation will be listed by treatment sequence and participant.

All SAEs will be listed by treatment sequence and participant.

#### ***10.4.6 Adherence and Retention Analyses***

The percentage of participants that complete the desired number of follow up blood collection points will be calculated and presented with 95% confidence intervals.

#### ***10.4.7 Baseline Descriptive Statistics***

Baseline characteristics will be calculated using mean, standard deviation, median, interquartile range, percentages and 95% confidence intervals (where appropriate).

#### ***10.4.8 Planned Interim Analyses***

##### **10.4.8.1 Safety Review**

As per AE reporting, AEs will be collated and reviewed semi-annually by the DSMB. This may include crude rates of type specific AEs; however, no formal interim analysis will be conducted.

##### **10.4.8.2 Efficacy Review**

No interim efficacy analysis will be performed.

#### ***10.4.9 Additional Sub-Group Analyses***

No sub-group analysis will be performed.

#### ***10.4.10 Multiple Comparison/ Multiplicity***

No adjustment will be made for multiple comparisons.

#### ***10.4.11 Tabulation of Individual Response Data***

Individual PK and safety data will be tabulated for each time point and included in the appendices of the final study report.

#### ***10.4.12 Exploratory Analyses***

No exploratory analysis will be conducted.

### **10.5 SAMPLE SIZE**

At the completion of the study, it is desirable that a minimum of 12 participants will complete a minimum of 75% blood collection time points.

### **10.6 SOFTWARE**

PK parameters are determined using Non-Compartmental Analysis embedded within Phoenix WinNonlin Pharmacokinetics software (Certara, Princeton, NJ).

## 11 SOURCE DOCUMENTS AND ACCESS TO SOURCE DATA/DOCUMENTS

Direct access to source data/documents will be provided to the Sponsor, trial-related monitoring, audits, NYSPI IRB, and regulatory inspection(s).

## 12 QUALITY ASSURANCE AND QUALITY CONTROL

QC procedures will be implemented beginning with the data entry system and data QC checks that will be run on the database will be generated. Any missing data or data anomalies will be communicated to the site(s) for clarification/resolution.

Following written SOPs, the monitors will verify that the clinical trial is conducted and data are generated, documented (recorded) and reported in compliance with the protocol, GCP and the applicable regulatory requirements (e.g., GLP & GMP).

The investigational site will provide direct access to all trial related sites, source data/documents and reports for the purpose of monitoring and auditing by the Sponsor, CRO and inspection by local and regulatory authorities.

## 13 ETHICS/PROTECTION OF HUMAN PARTICIPANTS

### 13.1 ETHICAL STANDARD

The study will be conducted in accordance with the guidelines and principles outlined in the International Conference on Harmonization - Standards of Good Clinical Practice and the Declaration of Helsinki. Compliance with these standards ensures that the rights, safety and well-being of participants are consistent with the above principles.

### 13.2 INSTITUTIONAL REVIEW BOARD

The investigator will obtain NYSPI IRB approval for this study. Initial IRB approval as well as all materials approved by the IRB for this study, including the participant consent form and recruitment materials.

Annual Reports describing the study progress and all AEs will be provided to the NYSPI IRB, along with a final study report by the PI. A copy of this report will also be provided to the Sponsor.

### 13.3 INFORMED CONSENT PROCESS

#### 13.3.1 *Consent/Accent and Other Informational Documents Provided to Participants*

All study participants will be provided with a Participant Information Consent (PIC) describing the study and providing sufficient information so that they are able to make an informed decision about their participation in the trial. The PIC form will be submitted with the research application for review and approval by the IRB.

#### 13.3.2 *Consent Procedures and Documentation*

The PI (or authorized designee) will ensure that the participant is given full and adequate oral and written information about the nature, purpose, potential and possible risks and benefits of the study. Each prospective participant will receive an IRB-approved PIC that summarizes

the pertinent study information and will be given ample time to read the form and ask questions about the study. All information is to be provided in a language understandable to the participant and must not include any language that waives the participant's legal rights. Prospective participants must also be informed of their right to withdraw consent without prejudice at any time during the study. If the participant chooses to participate, he/she must sign the PIC before any study-specific procedures are conducted.

### **13.4 PARTICIPANT AND DATA CONFIDENTIALITY**

All data generated in this study will remain confidential. All information will be stored securely. Participant information will only be disclosed to authorized individuals i.e. research personnel listed on the Delegation of Authority Log who have signed a confidentiality agreement with the PI to undertake research related procedures.

All participant data will be de-identified by use of an alphanumeric study coding system. Participant identification will be recorded on a Master Participants List held in-confidence by the PI in a locked cabinet separate to the de-identified data sheets.

Personal information recorded in study documentation or an electronic database will only be accessed by authorized study personnel. Personal computer access will be password protected and also limited to authorized study personnel.

#### ***13.4.1 Research Use of Stored Human Samples, Specimens or Data***

##### **13.4.1.1 Naltrexone bloods**

All NTX blood samples will be collected in 1 x 10 mL Na Heparin tubes (9 mL) and stored in the study site refrigerator at 0-4°C until specimen preparation.

Specimen preparation will be carried out at study site within 24 hours. This will involve centrifugation of the blood sample to enable plasma separation. Plasma will be extracted and stored in suitable containers (1.5 mL Eppendorf's) and stored at -80°C. When batches of greater than 50 samples are available these can then be shipped on dry ice to Xenobiotic Laboratories for analysis. Backup samples will remain stored at Clinilabs for the duration of the trial. All samples will be analyzed for free (unconjugated) NTX and free (unconjugated) 6 $\beta$ N quantification. It is anticipated that samples will be prepared and split into 4 aliquots, with 2 being used for analysis and 2 serving as a backup being stored de-identified in a -80°C freezer. Samples will be kept for 5 years after the completion of the trial, after which time they will be destroyed.

### **13.5 FUTURE USE OF STORED SPECIMENS**

Data collected for this study will be analyzed and stored at study site, as per the site's standard protocols.

## 14 DATA HANDLING AND RECORD KEEPING

### 14.1 DATA COLLECTION AND MANAGEMENT RESPONSIBILITIES

An electronic Case Report Form (eCRF) will be designed to record data required by the protocol and collected by study personnel. An eCRF will be completed for each participant.

A confidential list of participant names, contact details, and screening numbers will be kept by the study site. eCRF data removed from the study site will be identified by the screening number and will not contain participant names or contact details.

Data collection is the responsibility of the clinical trial staff at the site under the supervision of the site PI. The PI is responsible for ensuring the accuracy, completeness, legibility and timeliness of the data reported. All source documents should be completed in a neat, legible manner to ensure accurate interpretation of data.

### 14.2 STUDY RECORDS RETENTION

Retention and storage of essential clinical study documents (e.g., worksheets, drug accountability forms, and other administrative documentation) shall be governed by the terms and conditions of NYSPI.

- Ten years after discontinuation of the study, or
- Two years following the date a marketing application is approved for the study drug for the indication for which it is being investigated pursuant to the study, or
- If no application is to be filed or if the application is not approved for such indication, until 2 years after the date the study is terminated.

Participants' medical files should be retained in accordance with the applicable legislation and in accordance with the maximum period of time permitted by the hospital, institution, or private practice

### 14.3 PROTOCOL DEVIATIONS

A protocol deviation is any noncompliance with the clinical trial protocol, SOP's and GCP requirements. The noncompliance may be either on the part of the participant, the PI, or the study site staff. As a result of deviations, corrective actions are to be developed by the site and implemented promptly.

The PI should not implement any deviation from, or changes of the protocol without agreement by the Sponsor and prior review and documented approval/favorable opinion from NYSPI IRB, except where necessary to eliminate an immediate hazard(s) to trial participants, or when the change(s) involves only logistical or administrative aspects of the trial (e.g., change in monitor(s), change of telephone number(s)).

If the PI implements a deviation from, or a change of, the protocol to eliminate an immediate hazard(s) to trial participants, without prior approval/favorable opinion from NYSPI IRB. As soon as possible, the implemented deviation or change, the reasons for it, and, if appropriate, the proposed protocol amendment(s) should be submitted:

- To NYSPI IRB for review and approval/favorable opinion,
- To the Sponsor for agreement and, if required,
- To the regulatory authority (e.g., FDA).

The PI, or person designated by the PI, should document and explain any deviation from the approved protocol.

